7.0 Study Timelines*

- 1. Describe: Patients in this Pilot Cohort will be in the research study for 6 weeks total including: a 4-week intervention period and 2-week post intervention period. Patients will use the app for a total of 4 weeks (4-week intervention period), and will complete surveys at baseline, 4 weeks (end of intervention period), and at 6 weeks (end of 2-week post intervention period).
 - We anticipate enrolling 1-2 patients per week during the pilot period, and should thus complete the study within 4-5 months.
 - 2. The study timeline may change due to unforeseen circumstances. The estimated date for the investigators to complete this study (complete primary analysis) is October 31, 2022.

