8.0 Study Endpoints*

8.1 ENDPOINT 1: The primary objective is to determine feasibility and acceptability of STAMP+CBT. Specifically, we will evaluate patients' adherence to daily and weekly comprehensive symptom selfassessments within the STAMP+CBT app. We will calculate patients' overall adherence rate and 95% confidence interval. Defined using precision analysis, we will consider the intervention to be feasible if >70% of subjects complete >4 of the 6 pain-CBT modules and completes 50% of surveys by the end of 4 weeks (completion of the 4week intervention study period; completion of the 2-week post intervention period will be exploratory).^{40,41} The intervention will be considered **acceptable** if >80% of the acceptability items are rated 4 or higher/5; lower ratings will lead to app refinements. Other feasibility measures will assess time to accrual, participation rates, study retention and completion rates, and the number of patients who continue to review app content between weeks 5-6 (post-intervention period). Power calculation: With 10 patients, we will be able to estimate these proportions with margins of error (half of a 95% confidence interval) of approximately 18% or less assuming that the feasibility threshold of 70% is reached. This margin of error is small enough so that proportion estimates relevant to study feasibility will be

accurate and provide informative guidance for future, larger studies. Using **qualitative** framework analysis methods, we will explore barriers/facilitators, suggested changes to content, acceptability of intervention engagement, and whether app use continues after completion. Although power is not sufficient in this pilot, we will explore associations between levels of engagement and changes in pain severity/interference, opioid use, catastrophizing, sleep, mood, and pain self-efficacy.

8.2 COMPREHENSIVE ENDPOINT: The study team will use qualitative and quantitative results to determine the feasibility and acceptability of this pain CBT mobile health app for patients with cancer. This feasibility study will inform final modification to the application and study procedures in preparation for a future efficacy study of the STAMP+ CBT mobile health app.

9 Procedures Involved*

9.1 STUDY PROCEDURES:

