Participants will include DFCI patients presenting to outpatient palliative care, GCC, or satellite (MV and LD) clinics with ongoing chronic cancer pain management issues. Participants will meet with the study team in person, over the phone, or via a compliant and secure video chat/screen- share platform (i.e. Zoom). We will conduct the pilot cohort with up to 15 patients. Each participant will receive a \$25 gift card upon completion of the 4-week intervention period, and another \$25 gift card upon completion of the 2-week post intervention survey. The first 5 patients will onboard to the application and their involvement/feedback will focus on making final revisions onboarding for the application and study procedures. Therefore, the following 10 patients' data will be included for pilot study analysis and feasibility findings.	 Use the STAMP+CBT mobile app for 4 weeks (intervention period, 4 weeks for content introduction, extended 2 weeks for review of content if patient's request this) Engage with pain CBT content including a goal-setting module, relaxation exercises, and educational content Daily and weekly reporting of pain, catastrophizing, mood, and sleep symptoms and painkiller usage and satisfaction through the app (Appendix U) Complete survey assessments at baseline, 4 weeks (end of intervention period), and 6 weeks (end of 2-week post intervention period) assessing pain severity, self-efficacy and catastrophizing, physical function, opioid use, and quality of life outcomes. (Appendices P, Q, R) End-of-intervention interview (4 weeks) assessing usability and acceptability (Appendix T)
	• Wedical Record Abstraction (Appendix O)

 Table 1. Brief description of pilot cohort activities

PILOT COHORT:

The first few patients (up to 5) will onboard to the application and their involvement/feedback will focus on making final revisions to the mobile application and study procedures. All procedures will be the same for the 15 patients, however, data for the initial patients (up to 5) will not be included in final analysis as their involvement will be focused on revising final app bugs/iterations and modifications to study procedures before the pilot trial initiation. The following patients (up to 10) will be considered as the core pilot study participants to evaluate feasibility and acceptability of the application and study procedures.

Survey assessments

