After the patient completes the baseline survey, the RA will meet with the patient (in person or virtually), to assist in either 1) downloading the application onto participants' mobile device or 2) providing/mailing the study phone to the participant. The RA will help to register the patient to the app and help set up any preferences. The RA will then conduct a 15-minute tutorial on the STAMP+CBT app and its intended use (Appendix S). The RA will also input the patient's pain medications from Epic, reconciling this list with the patient, and with the nurse navigator on the patient's care team if there are any discrepancies. As the nurse navigator is already a member of the care team, they'll have access to all Epic records and any documentation for this study included in Epic. The participant will also input their desired goal to work towards for the duration of the trial. During the trial, there is also a function in the app that allows participants to notify the research team if a medication or goal needs to be changed and reflected in the app. Final iterations to the app, research portal, and study procedures will be made following the initial few patients (up to 5) recruited to using the application. Thereafter, we will begin recruiting patients (up to 10) for the pilot study cohort.

Participants will utilize STAMP+CBT for 4-weeks (intervention study period). The 4 weeks will consist of all content introductions. Patients will also be offered the opportunity to continue their app use for the next 2 weeks (post-intervention period) until study completion (2 week follow up and survey), this will allow us to assess feasibility and acceptability of the appropriate length of use for the intervention. STAMP+CBT hosts and organizes patients' opioid/non-opioid analgesics. It has an extensive multi-media library of education content related to pain management (Appendix C)

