- 11.2 Statistical analyses will be utilized in the pilot intervention portion of this study to ascertain feasibility and acceptability. We will measure time spent on the app per day and per week, completion rates for surveys and content review, and frequency of log-ons over the course of the pilot. The primary objective is to determine feasibility and acceptability of STAMP+CBT. Defined using precision analysis, we will consider the intervention to be feasible if >70% of subjects complete \geq 4 of the 6 pain-CBT modules and patients will complete 50% of surveys by the end of 4-weeks (completion of the 4-week intervention study period and completion of the 2-week post intervention period).^{40,41} A module will be considered complete if the participant engages in >70% of its content, including completing mHealth survey items, psycho-educational content, and app exercises. The intervention will be considered acceptable if >80% of the acceptability items are rated 4 or higher/5; lower ratings will lead to app refinements. Other feasibility measures will assess time to accrual, participation rates, and study retention and completion rates. Power calculation: With 10 patients, we will be able to estimate these proportions with margins of error (half of a 95% confidence

interval) of approximately 18% or less assuming that the feasibility threshold of 70% is reached. This margin of error is small enough so that proportion estimates relevant to study feasibility will be accurate and provide informative guidance for future, larger studies. Although power is not sufficient in this pilot, we will explore associations between levels of engagement and changes in pain severity/interference, opioid use, catastrophizing, sleep, mood, and pain self-efficacy.

- 11.3 The data the research team will access regarding app utilization will include; date and time of app log-ins, date of time of survey completion, survey responses, including clinical reporting of daily symptoms and medication usage, total app log-ins during intervention period, percent of surveys completed during intervention period, date time and frequency patients access external educational content.
- 11.4 PHI data will be collected using REDCap and the STAMP+CBT app.

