- 12.2 Protection against psychological risks: if in the course of their participation patients raise significant emotional distress, the appropriate care team members i.e. nurse navigator, physician, midlevel provider will be contacted to make appropriate social work or mental health referrals. Similar to that of physical risks, this app provides closer monitoring than what is provided for usual care for psychosocial needs; In addition to instructing patients to call their care team for advice, the RA will share patient's elevated symptoms with a nurse navigator, already assigned to patients' care teams, for follow up. As such, these nurse navigators, will have access to all health records and including any documentation for this study included in EPIC.
- 12.3 Protection against privacy risks: To monitor the risk of loss of confidentiality/privacy, the study team has ensured that the STAMP+CBT app is HIPPA compliant and meet the privacy and security standards set by DF/HCC. In addition, all collected study data will be maintained in a secure location and personal identifiers will be removed.

12.4 To maximize data security, both REDCap and STAMP+CBT employ:

- User Privileges To ensure that users have access only to data and information that they are supposed to have within the application, user privileges are utilized within the software. Each user has their own account, and their user account will only have access to information that they themselves have created or to which administrators have granted them access.
- Password-protection & Authentication Both systems are password protected and implement authentication to validate the identity of end-users that log in to the system.
- Logging and Audit Trail Both systems maintain built-in audit trails that log all user activity and all pages viewed by every user.
- 12.5 Institutions will register eligible participants in the Clinical Trials Management System (CTMS) OnCore as required by DF/HCC Policy REGIST-101.

13 Withdrawal of Subjects*

- *13.1* Subjects who do not complete app onboarding within 3 weeks of study enrollment will be withdrawn from the research study without their consent.
- 13.2 These patients will be informed of their withdrawal from the study by study staff. The overall DF/HCC study PI, [name],

will make all decisions regarding early termination of the study. The study team will then notify all participants accordingly.

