Once approved to approach, the study staff may approach patients in-person during clinic. Once approached the RA will review the study letter and consent form with the patient (Appendices X and AD). If it is not possible for the RA to meet the patient during a clinic visit, the clinician may introduce the study and the RA will follow up by phone. During a phone call the RA will explain the study and offer participation before obtaining written informed consent. During this phone call, the RA will email a copy of the study letter and consent form and the participant will provide written consent. The RA will send the study letter and consent forms through a secure and personalized link in the FDA and HSSH compliant Mass General Brigham/Partners REDCap database. The RA will attempt to contact a patient three times. If contact is not established, the RA will email a copy of the recruitment letter to introduce the study (Appendix AC). The letter encourages the patient to contact the research team if they are interested in participating in the study. If the patient then contacts the research team, the study letter and consent form will be reviewed remotely during a phone call with the patient before obtaining written consent. If the RA is

unable to establish contact with the patient after 3 call contacts and if the patients does not respond to the email recruitment letter, the patients will no longer be contacted

All interested participants will provide written consent after thorough review of the study letter and consent form. Next, they will complete the baseline survey to ensure enrollment in the study. Thereafter, the RA will coordinate with the patient to onboard with the pilot application. They will be notified that participation is completely voluntary and can be stopped at any time for any reason.

27 Process to Document Consent in Writing

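### Could enrolled patients withdrawn for not onboarding drop out of the >70% feasibility denominator?

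*Combined protocol and SAP*

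**What the plan says.** The feasibility rule is in Section 8.1: "we will consider the intervention to be feasible if >70% of subjects complete >4 of the 6 pain-CBT modules", together with half of the surveys by the end of week 4. Section 11.2 repeats it with the same subject of the sentence: "we will consider the intervention to be feasible if >70% of subjects complete". Neither section defines an analysis set.

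The withdrawal rule is in Section 13.1: "Subjects who do not complete app onboarding within 3 weeks of study enrollment will be withdrawn from the research study without their consent".

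Enrolment comes before onboarding. After consent, Section 26 says: "Next, they will complete the baseline survey to ensure enrollment in the study". Onboarding is arranged after that. In Section 9 (Intervention) it is a step done with the research assistant: "The RA will help to register the patient to the app and help set up any preferences". A patient removed under Section 13.1 is therefore already enrolled but has no app account.

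The one stated exclusion from analysis is in Section 9 (Pilot Cohort): "data for the initial patients (up to 5) will not be included in final analysis". The patients after them, up to 10, are described by recruitment and are the group in which feasibility is judged. No section says whether a patient withdrawn under 13.1 is replaced.

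Section 11.3 lists the app-utilization data the team will access, including "percent of surveys completed during intervention period". Section 7.0 says patients "will be in the research study for 6 weeks total including: a 4-week intervention period", the remaining two weeks being the post-intervention period.

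**The concern.** Failing to get onto the app is itself a feasibility failure. If the rate were computed from an app export, patients who never onboarded would be missing from it without anyone having decided to exclude them, and the rate could only rise. With 10 patients and a strict bar, one patient matters.

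Two features of the document seem to support an onboarded-only denominator. The survey percentage in 11.3 refers to an intervention period that a patient who never onboarded does not have. And the six weeks in 7.0 are made up of 4 + 2 weeks, leaving no room for the three weeks that 13.1 allows before onboarding (3 + 4 + 2 = 9). At stake is the pre-set feasibility statement.

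**Working it through.** **Inputs from the documents.** Core cohort of 10 (8.1, 9, 11.2); strict >70% (8.1, 11.2); withdrawal if not onboarded within 3 weeks (13.1). The plan gives no figure for non-onboarding or withdrawal, so there is nothing of its own to reproduce on this point.

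**Assumptions.** Success rate p among onboarded patients of 60%, 70% or 80%. Non-onboarding rate q of 2%, 5% or 10%.

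**Step 1: where the verdict can differ.** Let w of 10 enrolled be withdrawn and x complete. The enrolled rate is x/10 and the onboarded rate is x/(10 − w). The fewest successes that exceed 70% are 8 of 10, 7 of 9 and 6 of 8.

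- w = 1: the verdicts differ only at x = 7 (7/9 = 77.8%, 7/10 = 70.0%).
- w = 2: they differ at x = 6 (6/8 = 75.0%, 6/10 = 60.0%) and x = 7 (7/8 = 87.5%, 7/10 = 70.0%).

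**Step 2: chance of those outcomes, given that the withdrawals have happened.**

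| | p = 60% | p = 70% | p = 80% |
|---|---|---|---|
| w = 1: P(Bin(9, p) = 7) | 0.161 | 0.267 | 0.302 |
| w = 2: P(Bin(8, p) = 6 or 7) | 0.299 | 0.494 | 0.629 |

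**Step 3: without conditioning on a withdrawal.** Hold the true rate among enrolled patients at 60%, so that onboarded patients succeed at 0.60/(1 − q) = 0.612, 0.632 or 0.667. With everyone counted, P(declared feasible) = P(Bin(10, 0.60) ≥ 8) = 0.167. In the second column, m onboard with m ~ Bin(10, 1 − q), and the rest are dropped without replacement. In the fourth, recruitment continues until 10 have onboarded. The last column is P(Bin(10, 0.60/(1 − q)) ≥ 8), which keeps n at 10 and so shows selection alone, without the shift of the bar from 8/10 to 7/9 or 6/8.

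| q | Declared feasible if dropped | Verdict differs, no replacement | Verdict differs, with replacement | Declared feasible, n held at 10 |
|---|---|---|---|---|
| 2% | 0.202 | 0.034 | 0.003 | 0.188 |
| 5% | 0.261 | 0.094 | 0.017 | 0.224 |
| 10% | 0.379 | 0.211 | 0.069 | 0.299 |

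With replacement and one withdrawal (10 onboarded, 11 enrolled) the verdicts agree at every x: 8/10 and 8/11 = 72.7% both pass, and 7/10 and 7/11 = 63.6% both fail. Two withdrawals are needed before they differ (8/10 = 80.0% against 8/12 = 66.7%).

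**Step 4: which denominator the text gives.**

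- 8.1, 11.2 and 13.1 all speak of subjects, and 13.1 applies the word to people who are enrolled but not onboarded.
- The core group is described by recruitment, and only the initial patients are excluded.
- The rule requires modules and surveys together. A patient who never onboarded has completed no modules and fails whatever the survey fraction is. An undefined 0/0 for surveys never has to be resolved. This holds whether the module limb is read as more than 4 (8.1) or at least 4 (11.2).
- 11.3 is a list of utilization data. It does not mention the 70% rule or a denominator, and it does not list module completion, the first limb of the rule.
- The six weeks in 7.0 describe the time of participation. Leaving out set-up time says nothing about who is counted.
- The chart-abstraction text in Section 9 notes that deaths can worsen the feasibility evaluation. That fits a denominator that keeps patients who cannot finish, though it does not address 13.1 directly.

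**The case for a change.** The strongest argument for a change is that 13.1 removes precisely the patients who did not start the app, that any error from dropping them is always in the favourable direction, and that naming the denominator before results are seen would cost one sentence. Retention is listed among the other feasibility measures and is not tied to the 70% rule, so it cannot correct the pre-set verdict. The sponsor also thought non-onboarding likely enough to write a rule for it.

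Much of this stands. The plan is silent on how these withdrawals count and on replacement, and the arithmetic is right. If patients were dropped without replacement at an assumed 10% non-onboarding rate, the verdict would differ about one time in five. What does not stand is that the plan directs the analyst to that result. No sentence ties the denominator to app records, and the wording points to enrolled patients. The large conditional figures also presuppose that a withdrawal has occurred, in patients who have already consented and completed a baseline survey, who are onboarded with the research assistant's help, and who are lent a phone if needed.

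**Conclusion.** No change is needed. This is a missing detail that an analyst following the text fills sensibly: enrolled core patients withdrawn under 13.1 stay in the denominator and, with no modules completed, do not meet the criterion. No stated rule gives a wrong result.

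If someone nonetheless dropped them without replacement, the verdict would differ with probability 3%, 9% or 21% at assumed non-onboarding rates of 2%, 5% or 10% and a true 60% among enrolled patients. With replacement to 10 onboarded, the figures are 0.3%, 1.7% or 6.9%. The documents supply none of these rates and no replacement rule, so the sizes are illustrations.

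The consequence is also contained. Participation, retention and completion rates are reported alongside (8.1, 11.2), so non-onboarding need not be hidden, and 8.2 draws its conclusion from qualitative and quantitative results together. The sensitivity to one patient comes from a strict 70% bar with 10 patients, and any single non-completer can have the same effect.
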